# History of revisions to the Phase 1 protocol.

The following table presents the noteworthy changes for each version of the Phase 1 protocol for (2R,6R)-Hydroxynorketamine.

Protocol			
Version	Date	Section	Description of Change
2.0	10/23/2020	Study	Updated the study contact information for the
		Contacts	pharmacokinetics lead to [name].
2.0	10/23/2020	9.3	Removal of relatedness aspects of the stopping
			rules.
2.0	10/23/2020	11.7	Removal of unnecessary details describing the
			IDP, Diluent and administration equipment. This
			information is contained within the MOP.
2.0	10/23/2020	11.9	Addition of reporting language for SAEs.
2.0	11/11/2020	11.9	Addition of capture of abuse-related AE's
3.0	3/3/2021	Study	Change in PK lead to [name]
		Contacts	
4.0	3/21/2022	Study	Change in study PI to [name]
		Contacts	
4.0	3/21/2022	Synopsis	Edits and additional details (cohort #, dose)
			around the MAD study protocols
4.0	3/21/2022	Synopsis	Additional of the CSF Capture study protocols
4.0	3/21/2022	Tables	Revised MAD study schedule of assessments
			and procedures
4.0	3/21/2022	Tables	Added CSF Capture study schedule of
			assessments and procedures
4.0	3/21/2022	Figures	Added Visual representation of MAD and CSF
			Capture study timelines
4.0	3/21/2022	TOC	Table of contents changes
4.0	3/21/2022	7.0	Addition of CSF Capture study design section
4.0	3/21/2022	Multiple	References to the CSF Capture study design
			added throughout multiple sections
4.0	3/21/2022	12.9	Addition of AE response procedures
4.0	3/21/2022	Tables	Addition of CSF Capture study blood draw
		11& 12	schedule and CSF draw schedule
5.0	5/24/2022		Corrections and Updates for consistency
6.0			Remove CSF Capture Cohort #10, revise Cohort
			#9
7.0	11/15/2023	Synopsis	Updated objectives to reflect study design

## SYNOPSIS

**Title:** A Double-Blind, Placebo-controlled, Single Ascending Dose (SAD), Multiple Ascending Dose (MAD) and CSF Capture Study of the Safety, Pharmacokinetics and Pharmacodynamics of (2R,6R)-Hydroxynorketamine in Healthy Volunteers

Sponsor: National Institute of Mental Health

Name of drug substance: (2R,6R)-Hydroxynorketamine hydrochloride

**Name of investigational drug product:** (2R,6R)-Hydroxynorketamine hydrochloride solution for injection

Clinical Phase: Phase 1

Clinical Site: Duke Clinical Research Institute, Duke University School of Medicine Objectives:

Primary:

• Determine the safe dose range of (2R,6R)-Hydroxynorketamine

• Determine the pharmacokinetics of (2R,6R)-Hydroxynorketamine administered in single ascending doses

• Determine the pharmacokinetics of (2R,6R)-Hydroxynorketamine administered in multiple ascending doses

Exploratory:

Collect quantitative electroencephalography (qEEG) data following administration of (2R,6R)-Hydroxynorketamine in healthy Subjects as a pharmacodynamic biomarker
Assess the concentration of (2R,6R)-Hydroxynorketamine in cerebral spinal fluid (CSF) following a single IV administration

## Methodology/study design:

A 6-cohort single ascending dose (SAD) study will be conducted in healthy volunteers utilizing a slow-infusion intravenous (IV) route of administration. Standard safety, pharmacokinetics (PK) and qEEG monitoring will be evaluated at all dose levels. Subsequently, a 2-cohort multiple ascending dose (MAD) study will be conducted. Doses will be administered on days 1,4, 8, and 11. Standard safety parameters will be monitored, and PK will be evaluated at all dose levels.

Finally, a single cohort of healthy volunteers will receive a single dose by slow-infusion IV and have PK samples collected from both blood and cerebrospinal fluid (CSF).

### Study drugs, formulation, dose and route of administration:

(2R,6R)-Hydroxynorketamine hydrochloride will be administered intravenously over a 40-minute period as a solution in a 25 mM sodium phosphate 0.9% w/v saline solution. The SAD doses will range from 0.1 mg/kg to 4.0 mg/kg and the investigational drug product will be diluted into a 53 mL total volume of formulant.

Placebo will be made up of a 0.9% w/v saline solution (53 mL total volume) also administered via slow IV infusion over a 40-minute period.

### Subjects:

A total of 48 Subjects are planned to be enrolled in a 6-cohort SAD study (36 in the treatment groups and 12 in the control groups). All SAD cohorts will have 6 Subjects in the treatment group and 2 Subjects in placebo group.

All cohorts in the SAD study will incorporate sentinel dosing which will include 1 active and 1 placebo Subject. All remaining Subjects will be dosed at least 24 hours after the sentinel cohort participants.

A total of 16 Subjects are planned to be enrolled in a 2 cohort MAD study (12 in the treatment groups and 4 in the control groups). All MAD cohorts will have 6 Subjects in the treatment group and 2 Subjects in placebo group.

A total of 6 subjects are planned to be enrolled in a 1 cohort CSF capture study. The CSF cohort will have 4 in the treatment group and 2 in the control group.

Additional cohorts (both SAD and MAD) may be enrolled if it is determined that an intermediate or higher dose level should be evaluated upon review of both safety and PK data. The Institutional Review Board will be notified of this revised approach.

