#### Table 5: MAD planned dosing levels
## 7.0 STUDY DESIGN (CSF CAPTURE)

The cerebrospinal fluid capture (CSF Capture) portion of the study is a 1-cohort single site, double-blind, placebo-controlled design assessing (2R,6R)-Hydroxynorketamine in healthy adult male and female volunteers. All Subjects in the CSF Capture study will undergo a screening period of up to 28 days to ensure that all eligibility requirements are met. Key baseline safety metrics will be taken during screening and on the first Day of confinement. Selected safety metrics will be collected during the on-drug portion of the study. A final safety assessment will be conducted via an outpatient visit and follow-up phone call.

The cohort will include 5 Subjects receiving drug and 3 Subjects receiving placebo. Each Subject will receive a total of 1 dose (drug or placebo) administered on day 1. Each Subject will only participate in a single dose level. Table 6 outlines the planned dosing level and number of Subjects in each cohort.

Each dose will be administered after Subjects have fasted overnight for at least 8 hours.

Safety monitoring and assessments will be performed as described in sections 8.7 and 12.8. AE monitoring and reporting will be performed as described in sections 8.7 and 12.8. Dosing may be stopped if any of the stopping criteria are met as described in section 10.3. Determination of whether to escalate to the next dose level if stopping criteria are met will be made by the PI in consultation with the Medical Monitor and the Study Sponsor.

Pharmacokinetic blood and CSF samples will be collected as described in section 8.6.

Cohort	Dose (mg/kg)	Subjects on Active Drug (n)	Subjects on Placebo (n)
1	0.25	5	3

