# **12.4 SUBJECT ASSIGNMENT AND CHECK-IN**

For the SAD part, 48 Subjects (6 cohorts of 8 Subjects) will be dosed according to the Time and Events Schedule for the SAD study (Table 1). For the MAD part, 16 Subjects (2 cohorts of 8 Subjects) will be dosed according to the Time and Events Schedule for the MAD study (Table 2). For the CSF Capture part, 8 Subjects (1 cohorts of 8 Subjects) will be dosed according to the Time and Events Schedule for the CSF Capture study (Table 3). Additional cohorts may be enrolled after evaluation if it is determined that intermediate or higher dose levels should be tested. The number of Subjects planned is considered sufficient to characterize the safety and PK in a first-in-human clinical trial. Each Subject will receive an assigned treatment based on the randomization schedule prepared by the clinical site.

Subjects in the SAD study will be randomized to receive either a single dose of active drug or a single dose of matching placebo. Subjects in the MAD study will be randomized to receive either a series of 4 doses of active drug or a series of 4 doses of matching placebo. Subjects in the CSF Capture study will be randomized to receive either a single dose of active drug or a single dose of matching placebo.

For Subjects in the SAD study, the maximum duration of the study from screening to end-of-study will be approximately 33 days. For Subjects in the MAD study, the maximum duration of the study from screening to end-of-study will be approximately 52 days. For Subjects in the CSF Capture study, the maximum duration of the study from screening to end-of-study will be approximately 33 days.

For the SAD, MAD and CSF Capture parts, an appropriate number of alternates will be included as judged by the PI. Alternates not used in a cohort may be dosed in future cohorts if eligibility criteria are re-confirmed.

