9.2 Pharmacodynamics Endpoints

A second primary objective for this study is to assess the pharmacokinetics (PK) of (2R,6R)-Hydroxynorketamine HCl. PK endpoint analyses are covered in the PK analysis plan.

9.3 qEEG Endpoints

The secondary objective of this study is to collect quantitative electroencephalography (qEEG) data as a PD biomarker. qEEG endpoint analyses are covered in the qEEG analysis plan.

10. Sample Size

A total of 48 Subjects are planned to be enrolled in a 6-cohort SAD study (36 in the treatment groups and 12 in the control groups).

All SAD cohorts will have 6 Subjects in the treatment group and 2 Subjects in placebo group. All cohorts in the SAD study will incorporate sentinel dosing which will include 1 active and 1 placebo Subject. All remaining Subjects will be dosed at least 24 hours after the sentinel cohort participants.

A total of 16 Subjects are planned to be enrolled in a 2 cohort MAD study (12 in the treatment groups and 4 in the control groups). All MAD cohorts will have 6 Subjects in the treatment group and 2 Subjects in placebo group.

A total of 8 subjects are planned to be enrolled in a 1 cohort CSF capture study. The CSF cohort will have 5 in the treatment group and 3 in the control group.

Additional cohorts (both SAD and MAD) may be enrolled if it is determined that an intermediate or higher dose level should be evaluated upon review of both safety and PK data. The Institutional Review Board will be notified of this revised approach.

11. Analyses and Reporting

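### The CSF cohort is given two sizes (6 or 8), two dose statements and two first post-dose CSF draw times

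*Protocol*

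**What the plan says.** **Size and split.** The Subjects part of the protocol synopsis reads "A total of 6 subjects are planned to be enrolled in a 1 cohort CSF capture study" and "The CSF cohort will have 4 in the treatment group and 2 in the control group". Protocol section 7.0 reads "The cohort will include 5 Subjects receiving drug and 3 Subjects receiving placebo", and Table 6 repeats 5 and 3. Section 12.4 reads "For the CSF Capture part, 8 Subjects (1 cohorts of 8 Subjects) will be dosed". SAP section 10 reads "A total of 8 subjects are planned to be enrolled in a 1 cohort CSF capture study" and splits them 5 and 3. SAP section 5.3 and its Table 3 also give 5 and 3.

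**Dose.** Protocol section 8.5 sets the CSF doses at two levels, 0.25 and 2.0 mg/kg. Section 7.0 says "Table 6 outlines the planned dosing level and number of Subjects in each cohort", and Table 6 has one row, at 0.25 mg/kg. SAP Table 3 is the same. Section 7.0 adds "Each Subject will only participate in a single dose level". The CSF dose in both synopses is masked and is not used here.

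**CSF draw times.** Section 7.0 says "Pharmacokinetic blood and CSF samples will be collected as described in section 8.6". Section 8.6 lists preinfusion, 1 hour and about 8 hours, counted from the start of infusion. Section 12.11 also refers to section 8.6, and its text gives predose, 1 hour and 8 hours postdose. Table 12, which belongs to section 12.11, lists preinfusion, end of infusion, and 8 hours after the start.

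**The concern.** Planned enrolment, allocation, dose and sampling time are basic design figures, and for this cohort each has two readings. It is the only cohort in which healthy volunteers have a spinal catheter placed, a procedure that protocol section 4.0 links to bleeding, infection and headache. How many people undergo it, and at what dose, is something an IRB and a site need to read one way only. The cohort's stated purpose is to measure drug concentration in CSF after a single dose, and dose and sampling time bear directly on that measurement. The Manual of Procedures, Pharmacy Manual and randomisation schedule are not part of the documents, so it is unknown whether the site received conflicting instructions.

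**Working it through.** **1. Size.** Each version adds up on its own: 4 + 2 = 6 in the synopsis, and 5 + 3 = 8 in sections 7.0 and 12.4 and in the SAP. The conflict therefore lies between sections. It is not a slip in one digit, because the total, the active count and the placebo count all differ.

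The SAD and MAD counts come from the protocol synopsis and SAP section 10. The three samples per subject, two of them post-dose, come from section 8.6.

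| Quantity | Synopsis | Sections 7.0, 12.4 and SAP |
|---|---|---|
| CSF subjects | 4 + 2 = 6 | 5 + 3 = 8 |
| Study total | 48 + 16 + 6 = 70 | 48 + 16 + 8 = 72 |
| Active | 36 + 12 + 4 = 52 | 36 + 12 + 5 = 53 |
| Placebo | 12 + 4 + 2 = 18 | 12 + 4 + 3 = 19 |
| Placebo share of CSF cohort | 2/6 = 33.3% | 3/8 = 37.5% |
| CSF samples | 6 × 3 = 18 | 8 × 3 = 24 |
| Post-dose CSF samples, active | 4 × 2 = 8 | 5 × 2 = 10 |

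Neither document gives a sample-size calculation for this cohort. Section 12.4 calls the numbers sufficient by judgement, so there is no power figure to reproduce.

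**2. Dose.** Section 8.5 names two doses, with ratio 2.0 / 0.25 = 8. Table 6 and SAP Table 3 place all 5 active subjects at 0.25 mg/kg and none at 2.0 mg/kg. Because each subject takes part at one dose level only, the same subjects cannot also supply the second dose. Section 8.5 therefore names a dose to which no subject is assigned.

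**3. First post-dose CSF draw.** The infusion lasts 40 minutes. Counted from its start, Table 12 places the draw at about 40 minutes and section 8.6 at 60 minutes: 60 − 40 = 20 minutes apart. These are not two names for one time, because Table 11 lists end of infusion and 1 hour as separate blood draws. For scale, section 8.6 allows ±5 minutes for blood PK samples in the first 8 hours; the gap is 20 / 5 = 4 times that. The documents state no separate window for CSF. The choice also decides which plasma sample is nearest in time to the CSF value. The 8-hour draw agrees between section 8.6 and Table 12.

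**Two editorial points, not counted in the conclusion.** The synopsis times its CSF draws post infusion. Read from the end of infusion, that would be about 40 + 60 = 100 and 40 + 480 = 520 minutes after the start, so the time origin needs stating. The lead sentence of SAP section 5.3 describes two cohorts, against its own one-row table and the single cohort described elsewhere in both documents.

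**The case against.** The strongest reply is that these are leftovers and that the text mostly points one way. On headcount, the synopsis paragraph stands alone against two protocol sections and two SAP sections. On dose, section 8.5 is rationale: it allocates nobody and creates no second cohort, while section 7.0 sends the reader to a one-row table. On timing, sections 8.6 and 12.11 and the synopsis all say 1 hour, and the exception is a row label in a table of draw volumes. The version 6.0 entry in the revision history, which removes one CSF cohort and revises the other, may explain how this arose. The totals of 70 and 72 are sums made here and are not printed in either document. Section 10.2 allows replacement, so the number dosed could differ from plan anyway. Most important, CSF concentration is an exploratory objective in the protocol (the SAP synopsis lists it as secondary), and the SAP's analyses are descriptive or exploratory.

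Most of this is accurate, and it limits the consequences. It does not remove the conflicts. The documents state no rule of precedence between sections, a majority of passages is not such a rule, and the revision entry gives no headcount, dose or draw time. The Manual of Procedures might settle the site's practice, but it cannot make the protocol and SAP agree.

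**Conclusion.** The concern holds on all three points: 6 (4 + 2) against 8 (5 + 3) subjects; 0.25 and 2.0 mg/kg against 0.25 mg/kg only; and a first post-dose CSF draw at about 40 against 60 minutes from the start of infusion. The last comparison assumes the planned 40-minute infusion. All the text relied on is current and unmasked.

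The effect on inference is small: no power figure, error rate or primary conclusion depends on this cohort. The point is nevertheless more than clerical, because sample size, allocation, dose and sampling time are figures on which enrolment, drug preparation and CSF collection rest. No view is taken on which values are right.

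**What to change.** The sponsor should choose one headcount and active/placebo split, one cohort count, one dose statement, and one set of CSF draw times counted from a single stated origin. The places to align are:

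- protocol synopsis (Subjects and Pharmacokinetics)
- protocol section 7.0 with Table 6
- protocol sections 8.5, 8.6 and 12.4
- protocol section 12.11 with Table 12
- SAP section 5.3 with Table 3
- SAP section 10

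The Manual of Procedures, Pharmacy Manual and randomisation schedule should be checked against the chosen values at the same time.

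The cost is text correction in both documents, plus an amendment if the approved number or dose statement changes. Protocol section 14.4 requires IRB approval before an amendment is implemented, except to remove an immediate hazard, and notification only for purely logistic or administrative changes. No analysis method changes.

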## Pharmacokinetics:

Serial PK blood samples will be collected during the SAD portion for each Subject receiving drug and placebo at 9 timepoints (preinfusion, end-of-infusion [approximately 40 minutes], 1, 2, 4, 8, 12, 24, and approximately 48 hr after the start of the infusion). Pharmacokinetic urine samples will be collected during the SAD study for each Subject receiving drug and placebo at set intervals following the initiation-of-infusion (0-4, >4-8, >8-12, >12-24 hr). Pharmacokinetic urine samples (up to 3 per subject) will be collected at key time intervals (0-4, >4-8h, >8-12h, >12-24h) after the start of infusion.

Serial PK blood samples will be collected for the first and fourth (last) dosing in the MAD study for each Subject receiving drug and placebo. Blood PK samples will be obtained at 8 timepoints (preinfusion, end-of-infusion [approximately 40 minutes], 1, 2, 4, 8, 12, and approximately 24hr after the start of the infusion). Two PK blood samples will be collected for the second and third dosing in the MAD study for each subject receiving drug and placebo at approximately 10 minutes predose and at the end of the infusion.

Serial PK blood samples will be collected for the single dose CSF capture study for each Subject receiving drug and placebo. Blood PK samples will be obtained at 8 timepoints (preinfusion, end-of-infusion [approximately 40 minutes], 1, 2, 4, 8, 12, and approximately 24hr after the start of the infusion). CSF samples will be obtained preinfusion, and at 2 timepoints (1h and 8 hours post infusion).

Blood and CSF samples will be analyzed for PK of (2R,6R)-Hydroxynorketamine using a LC/MS/MS method to capture the following parameters: maximum plasma concentration ( $C_{max}$ ), time to  $C_{max}$  ( $t_{max}$ ), minimum plasma concentration ( $C_{min}$ ), area under the plasma concentration-time curve from 0 to infinity (AUC0- $\infty$ ), area under the plasma concentration-time curve during the dosing interval (AUC0-Tau), systemic plasma clearance (CL), volume of distribution during terminal phase ( $V_z$ ), renal clearance (CLR), terminal half-life ( $t_{1/2}$ ).

## Safety:

Safety will be assessed throughout the study. Baseline and follow-up safety assessments will include height, body mass index (BMI), weight, temperature, medical, visual and ocular history, physical examinations, ocular examinations, visual acuity, color vision tests, electrocardiograms (ECGs), vital signs (VS), clinical laboratory tests (hematology, serum chemistry, and urinalysis), the Profile of Mood States (POMS), the Columbia-Suicide Severity Rating Scale (C-SSRS), the Clinician Administered Dissociative States Scale (CADSS), and adverse events (AEs). Safety assessments will include AEs, ECGs, VS, clinical laboratory results, and physical observations. Assessment of each Subject's level of alertness/Sedation will be accomplished using the Modified Observer's Assessment of Alertness/Sedation (MOAA/S).

Evaluation of safety in the MAD study will utilize the same safety assessments used in the SAD study.

Evaluation of safety in the CSF capture study will utilize the same safety assessments used in the SAD and MAD study with the exception of the CADSS and MOAA/S assessments.

Monitoring of AEs will be governed by change from baselines established during prescreening and Day -1 examinations and clinical laboratory tests. AEs will be coded using the Medical Dictionary for Regulatory Activities (MedDRA) and summarized by system organ class and preferred term, by severity, by relationship to study drug and study procedure, and by study drug dose.

Dose escalation in the SAD study or continued dosing in the MAD study may be stopped according to the predefined halting rules or if a Subject's scores demonstrate acute suicidality on the C-SSRS assessment or at the discretion of the study Principal Investigator and/or sponsor.

Determination of whether to escalate to the next dose level in the SAD study or continue dosing in the MAD will be made by the Principal Investigator in consultation with the Medical Monitor and Study Sponsor.

## Test products, dose, and mode of administration for SAD study:

Cohort 1: (2R,6R)[contact] mg/kg via slow IV infusion (40 minutes) Cohort 2: (2R,6R)[contact] mg/kg via slow IV infusion (40 minutes) Cohort 3: (2R,6R)[contact] mg/kg via slow IV infusion (40 minutes) Cohort 4: (2R,6R)[contact] mg/kg via slow IV infusion (40 minutes) Cohort 5: (2R,6R)[contact] mg/kg via slow IV infusion (40 minutes) Cohort 6: (2R,6R)[contact] mg/kg via slow IV infusion (40 minutes)

## Test products, mode of administration and schedule for MAD study:

Cohort 1: (2R,6R)[contact] mg/kg via slow IV infusion (40 minutes) on days 1, 4, 8, 11 Cohort 2: (2R,6R)[contact] mg/kg via slow IV infusion (40 minutes) on

Cohort 2: (2R,6R)[contact] mg/kg via slow IV infusion (40 minutes) on days 1, 4, 8, 11

## Test products, mode of administration and schedule for CSF capture study:

Cohort 1: (2R,6R)[contact] mg/kg via slow IV infusion (40 minutes)

Control product (placebo) will be sterile saline also administered via slow IV infusion (40 minutes).

The highest dose administered in the MAD will not exceed the highest tolerable SAD dose.

### **Duration of patient participation in study:**

Participants in the SAD study: each Subject will participate in one treatment period. A treatment period consists of residential stay on days -1 to 2 inclusive with 1 follow up visit (Day 3) and phone call (Day 5-8).

Participants in the MAD study: each Subject will participate in one treatment period. A treatment period consists of residential stay on days -1 to 5, with discharge the morning of day 5 and re-admission on day 712 inclusive with 1 follow up phone call (Day 15) and phone call (Day 17-19).

Participants in the CSF capture study: each Subject will participate in one treatment period. A treatment period consists of residential stay on days -1 to 2 inclusive with 1 follow up visit (Day 3) and phone call (Day 5-8).

